If randomized to the overdose notification group, physicians who prescribed a qualifying prescription to the deceased or surviving patient in the year prior to their overdose will be informed of the overdose via letter. The letters will alert prescribers to the patient's opioid-related overdose, recommend the use of their state's PDMP, and list evidence-based interventions to lower opioid-related overdoses (Appendix 2 and 3).

Controls. Clinicians in the control group will receive guideline education in the form of the CDC pocket guide and no notification of a patient overdose event (See Appendix 5). https://www.cdc.gov/drugoverdose/pdf/TurnTheTide_PocketGuide-a.pdf

D. Statistical Analysis Plan

Patients who experienced an opioid overdose will be randomized to either the letter intervention or control. We will analyze how the prescribing behavior of those patients' clinicians changed pre-to-post intervention. We will use means and medians for continuous measures for sample descriptive statistics, frequencies for count data and standard deviations, and interquartile ranges for variance. We will evaluate changes in opioid prescribing rates by group using an intent-to-treat difference-in-differences regression model on clinician hydrocodone morphine equivalent weekly dose. The coefficient for the group assignment, overdose type, and time interaction, also known as the difference-in-differences estimator, denotes the change over time in 5 MME hydrocodone pills for prescribers in the intervention group compared to prescribers in the control group for both fatal and nonfatal overdose victims. The use of a mixed-effects hierarchical knotted spline Poisson regression model offers a flexible way to accommodate non-linear trends in prescribing by group before and after introducing the intervention. This model places a knot at the intervention start date allowing slopes before and after the introduction of the intervention to vary for each group. Our primary outcome is the daily average number of 5 MME hydrocodone pills. If we have an excess of data clustering at zero, indicating weeks during which a physician wrote no opioid prescriptions, we will use a zero-inflated or left-censored regression. The regression model estimating the association between letter assignment and weekly 5 MME hydrocodone pills prescribed is shown in Eq. 1:

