$$(pills)_{ijk}^* = \beta_1 + \beta_2 Time_{ij} + \beta_3 (Time_{ij} - t^*) + \beta_4 Group_i + \beta_5 Overdose Type_k + \beta_6 Group_i * Overdose Type_k + \beta_7 Time_{ij} * Group_i + \beta_8 (Time_{ij} - t^*) * Group_i + \beta_9 Time_{ij} * Overdose Type_k + \beta_{10} (Time_{ij} - t^*) * Overdose Type_k + \beta_{11} Time_{ij} * Group_i * Overdose Type_k + \beta_{12} (Time_{ij} - t^*) * Group_i * Overdose Type_k + \eta + \delta_{i(k)} + error$$

where $(pills)_{ijk}^*$ denotes the dependent variable for clinician i in week j , $Time_{ij}$ is the study week indexed by j , t^* is the spline knot for the start of the intervention, $(Time_{ij} - t^*)$ is a truncated line function that is equal to $(Time_{ij} - t^*)$ when $Time_{ij} > t^*$ and 0 otherwise to allow for nonlinear trends in prescribing following the intervention, $Group_i$ is dichotomous for the overdose notification intervention group, $Overdose Type_k$ is dichotomous for a fatal overdose, η is the clinic random effect, and $\delta_{i(k)}$ is the random effect for each clinician i who prescribed to patient k who suffered an overdose.

The mixed logistic regression model for our secondary outcomes is shown in Eq. 2:

$$(high dose Rx)_{ijk} = \beta_1 + \beta_2 Time_{ij} + \beta_3 Group_i + \beta_4 Overdose Type_k + \beta_5 Group_i * Overdose Type_k + \beta_6 Time_{ij} * Group_i + \beta_7 Time_{ij} * Overdose Type_k + \beta_8 Time_{ij} * Group_i * Overdose Type_k + \eta + \delta_{i(k)} + error$$

where $(high\ dose\ Rx)_{ijk}$ is whether the visit had a high dose prescription of 50 MME or greater (yes vs. no) for clinician i , $Time_{ij}$ is the study period (pre- vs. post-intervention) indexed by j , $Group_i$ is dichotomous for the overdose notification intervention group, $Overdose\ Type_k$ is dichotomous for a fatal overdose, η is the clinic random effect, and $\delta_{i(k)}$ is the random effect for each clinician i who prescribed to patient k who suffered an overdose. We will compute the estimated pre- to post-intervention change in the mean proportion of high dose patient visits for each of the four intervention groups: nonfatal control, nonfatal letter, fatal control, fatal letter. The proportion will be calculated by dividing the total number of patient visits where an opioid of at least 50 MME was prescribed by the total number of opioid prescriptions.

E. Privacy of Individuals and Confidentiality of Data

We will utilize two types of data for this study:

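### The SAP contradicts itself on the primary outcome unit, its Poisson model does not match Eq. 1, and it states no inference at the randomised overdose cluster

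*Combined protocol and SAP*

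**What the plan says.** **Model.** Section D commits to a Poisson spline: "The use of a mixed-effects hierarchical knotted spline Poisson regression model offers a flexible way to accommodate non-linear trends in prescribing by group". It reads the key coefficient additively: "The coefficient for the group assignment, overdose type, and time interaction, also known as the difference-in-differences estimator", which "denotes the change over time in 5 MME hydrocodone pills for prescribers in the intervention group". For excess zeros, "indicating weeks during which a physician wrote no opioid prescriptions, we will use a zero-inflated or left-censored regression".

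**Unit.** The sentence naming the primary outcome says: "Our primary outcome is the daily average number of 5 MME hydrocodone pills". Shortly afterwards: "The regression model estimating the association between letter assignment and weekly 5 MME hydrocodone pills prescribed is shown in Eq. 1". Under Eq. 1 the left-hand side "denotes the dependent variable for clinician i in week j". The synopsis and primary hypothesis 1 in Section B.a use weekly MME.

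**Random effects and randomisation.** Eq. 1 has a clinic effect and a second effect which "is the random effect for each clinician i who prescribed to patient k who suffered an overdose". Section C.b (Randomization and Allocation) randomises overdose clusters. Each cluster holds every clinician who prescribed an included drug to the overdose patient in the preceding year. A clinician who falls in several clusters is assigned at random to one of the patients.

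The text supplied gives no standard-error method, overdispersion term, small-sample correction, alpha, cluster count or cluster size.

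**The concern.** A Poisson mixed model has a log link and a rate-ratio coefficient. Eq. 1 is written on the outcome itself, with a star, an additive error and a coefficient in pills, so it could equally describe a linear or left-censored model. The choice matters because a plain Poisson likelihood takes the variance to equal the mean in whatever unit is used. Recording the same prescribing in a larger unit makes the data look more informative.

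The second issue does not depend on the first. The letter effect is a change in slope at the knot. Clinic and clinician intercepts absorb differences in level only. Nothing stated lets slope changes vary between clinicians or be correlated within the randomised cluster. Two analysts following different sentences could therefore report different primary p-values from the same data.

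**Working it through.** The documents state no power, alpha or sample-size figure, so there is none to reproduce. A two-sided 5% test is assumed throughout.

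**1. Unit factors.** The CDC pocket guide in the appendix equates 10 hydrocodone tablets with 50 MME, so one pill is 50/10 = 5 MME. If W is weekly pills, the daily average is W/7 and weekly MME is 5W.

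**2. Effect on z, plain Poisson with model-based standard errors.** Multiplying the outcome by c leaves the slope coefficient unchanged and multiplies the information by c, so z is multiplied by √c.

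| Change of unit | c | z multiplied by |
|---|---|---|
| daily pills to weekly pills | 7 | 2.65 |
| weekly pills to weekly MME | 5 | 2.24 |
| daily pills to weekly MME | 35 | 5.92 |

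Thus z = 1.0 (p = 0.32) in daily pills becomes 2.65 (p = 0.008) in weekly pills and 5.92 (p < 0.0001) in weekly MME. An exact Poisson–gamma random-intercept model fitted to one simulated data set gave the same coefficient (0.00265) in all three units, with z = 0.081, 0.213 and 0.476.

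**3. Direction of the error.** Assume independent prescriptions of b pills. The true standard error divided by the model-based one is √(b × f), with f = 1/7, 1 or 5, and the false-positive rate is 2(1 − Φ(1.96/ratio)). For b = 10:

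- daily: ratio √(10/7) = 1.195, 10.1%
- weekly pills: ratio √10 = 3.162, 53.5%
- weekly MME: ratio √50 = 7.071, 78.2%

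The direction is not fixed. With very regular refills, simulated true-to-model ratios on the weekly-pill scale were 0.57 to 0.68, so the model-based standard error is too wide. With looser 4-weekly 30-pill refills (±0.75 week, 10% missed), plain Poisson rejected in 1.2% (daily), 36% (weekly pills) and 69% (weekly MME) of runs.

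**4. If the error term in Eq. 1 is observation-level overdispersion.** In one simulated data set z was −0.16, −0.15 and −0.15 across the three units, against −0.20, −0.52 and −1.17 for plain Poisson. The unit dependence nearly disappears.

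**5. Correlation within the overdose cluster.** With m clinicians per cluster, DEFF = 1 + (m − 1) × ICC and actual alpha = 2(1 − Φ(1.96/√DEFF)). Both m and ICC are assumed:

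- m = 1.2, ICC 0.01: DEFF 1.002, alpha 0.050
- m = 2, ICC 0.1: DEFF 1.10, alpha 0.062
- m = 5, ICC 0.3: DEFF 2.2, alpha 0.186

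**6. Variation in clinicians' slope changes, linear reading.** The group × overdose type × slope-change term was simulated with 26 weeks before and 26 after. Mean volume was 8 prescriptions a week (Section B.b, Northwestern: 12,552/387 = 32.4 patients per clinician, refilled every 4 weeks). Model-based rejection was 5.1% with no variation. It was 6.7%, about 14% and 28.3% when the 26-week log-rate change varied between clinicians with SD 0.15, 0.3 and 0.5.

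**7. Cluster-robust standard errors.** With slope-change SD 0.3 between clinicians and 0.1 between clusters, results at 10+50, 20+40, 40+80 and 80+160 fatal + nonfatal clusters were:

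- CR2 with Satterthwaite df, Poisson: 4.2, 4.8, 4.9, 5.7%
- CR2 with Satterthwaite df, linear: 3.7, 4.9, 5.1, 5.7%
- clustered, normal reference: 9.9, 6.6, 5.8, 6.3%

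**The case against.** **Eq. 1's error term may be overdispersion.** On that reading the unit hardly matters (step 4). This stands. A reader might infer that any Poisson fit with model-based standard errors makes the p-value depend on the unit. The documents do not support that, because Eq. 1 carries an error term that could prevent it. They do not say that it does.

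**The missing link is only notation.** Eq. 2 is introduced as a mixed logistic model and is also written without a link and with an error term. This weakens any argument from the link alone. The additive reading in pills and the unexplained star remain.

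**The unit conflict is lopsided.** One sentence says daily; the rest of Section D, Eq. 1 and Section B.a are weekly. This is true, but it is the sentence that names the primary outcome. Weekly pills and weekly MME also still differ fivefold.

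**The simulated error rates do not size the cluster omission.** A reader might take the 7%, 14% and 28% in step 6 as the cost of ignoring the randomised unit. They come from assumed variation between clinicians. With between-cluster SD 0.1 and 80+160 clusters, clinician-level robust standard errors rejected 6.8, 5.7 and 5.8% in three settings, and overdose-cluster ones 5.8, 5.4 and 5.9%. The cluster itself cost at most about 1 point there.

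**Support for CR2 is limited.** It was tested with clinician intercepts conditioned out, not on the named mixed-effects, zero-inflated or left-censored models, and not every setting was run under both readings. Prescription volume was based on Northwestern; AltaMed's 17,674/134 = 132 patients per clinician was not used. All of this stands.

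**Conclusion.** Two statements rest on the text alone. The primary outcome has three incompatible units, and the named model does not match Eq. 1 or the stated meaning of its coefficient. The trial randomises overdose clusters, while the stated random effects are clinic and clinician intercepts, so neither within-cluster correlation nor variation in slope change enters the standard error of the letter effect.

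The √7, √5 and √35 ratios are exact algebra, but conditional on plain Poisson, model-based standard errors and no overdispersion term. A reader might also infer that such standard errors are always too small on the weekly scales. They are too small when multi-pill prescriptions arrive irregularly, and can be too wide on the weekly-pill scale when refills are very regular.

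The size of the cluster part cannot be fixed from the documents. It may be small if clusters hold one or two clinicians. The error rates above are illustrations driven mainly by assumed prescription size and slope variation. Because this is the primary analysis and the SAP does not determine which test is run, it should be corrected before the primary model is fitted.

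**What to change.** - **Unit.** State one outcome unit throughout. Weekly pills, as in Eq. 1, needs the fewest edits.
- **Model.** Name one model and make the link, the star, the error term and the coefficient interpretation in Eq. 1 agree with it. Say whether the error term is observation-level overdispersion.
- **Inference.** Base the primary test on a method that is valid at the randomised overdose cluster and does not depend on the unit. One example is standard errors clustered on the overdose patient to whom each clinician is assigned, with a small-sample correction such as CR2 and Satterthwaite degrees of freedom. An equivalent cluster-level method would also do. The chosen method should be checked on the model actually fitted.
- **Support.** Add a permutation test that re-randomises overdose clusters within health system. It addresses only the null of no letter effect and was not simulated here.

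**Cost.** The change is to SAP wording and analysis code; conduct, data and randomisation are unaffected. Intervals may widen where clinicians' trends differ: the simulated true standard error was 1.07 to 1.86 times the linear model-based one for slope-change SD 0.15 to 0.5. Section B.c excludes Los Angeles fatal overdoses, so the fatal contrast rests on Northwestern fatal clusters and may have few degrees of freedom (about 7 to 8 with 10 such clusters). Some settings remained mildly anti-conservative, up to 6.6%.

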The goal of the project is to dampen the intensity and frequency of opioid prescribing and to increase awareness and use of medication assisted therapy for persons with opioid use disorder through a cluster randomized trial. Overdose notification letters (See Appendix 2 and 3) will be sent to primary care clinicians randomized to the experimental study arm and meeting inclusion criteria at AltaMed Health Services or Northwestern Medicine. Both letters will include "if/when/then" language which advises the clinician to keep the letter's recommendations close when their next patient presents with pain. Clinicians notified of their patient's overdose will be compared to a control group receiving guideline education and no notification of their patient's overdose (Appendix 6). To quantify the effect of the notification letter, we will measure the change in clinician weekly milligram morphine equivalent (MME) prescribed to all of their patients in 6-month periods before and after receiving overdose feedback letters. The secondary outcomes include the change in proportion of patients prescribed at least 50 daily MME, buprenorphine referrals for medication assisted therapy, and access rates for referral links included in the letter.

Because the letters include patient identifying information linked to outpatient prescribing records, we requested a HIPAA waiver of authorization to match outpatient records to mortality and non-fatal overdose records. The research could not feasibly be conducted if research participants' authorization were required. AltaMed will release information under the auspices of a waiver of HIPAA authorization. USC and AltaMed have a fully executed Business Associates Agreement, Memorandum of Understanding and Data Use Agreement; Northwestern and IDPH and USC and Northwestern have a fully executed Data Use Agreement. AltaMed and Northwestern will cede to the County IRB as the IRB of record for this study.

To create the list of overdose patients for whom opioids were prescribed, outpatient records will be linked to the emergency department and, in the case of Northwestern patients, IDPH death records. Overdose data will be linked with outpatient records using matching software that complies with institutional security and privacy standards at IDPH and Los Angeles County. Where an existing direct link code is available (e.g. MRN), we will use the code.

Primary hypotheses:

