1. Clinicians randomized to the overdose notification group will exhibit a greater reduction in weekly MME from the pre- to post-period compared to clinicians randomized to the control group for fatal and non-fatal overdoses.
2. Among the clinicians who prescribed at least one opioid in the study period, those randomized to the overdose notification group will exhibit a greater reduction in the proportion of a clinician's patients prescribed at least 50 daily MME from the pre- to post-period compared to clinicians randomized to the control group for fatal and non-fatal overdoses.

b) Number of subjects:

AltaMed Health Services is a private health system in Los Angeles, California. AltaMed has 35 clinics with 134 clinicians with 17,674 such patients. Clinicians meeting inclusion criteria will be enrolled in the study. Northwestern Medicine is a regional health system affiliated with an academic medical center located in the Chicago region of Illinois and includes 60 primary care clinics that contain 387 clinicians with 12,552 patients using chronic opioid therapy for noncancer pain—on opioids for greater than three months.

c) Mechanism for subject selection or exclusion:

Eligible physicians and patients will be identified using outpatient opioid prescribing data

from electronic medical records. A clinician is eligible for inclusion if: 1) s/he prescribed a qualifying scheduled drug to a patient in the 12 months prior to their fatal or non-fatal overdose 2) the patient is 18 years old or older at the time of the overdose, 3) s/he practices within a health system enrolled in the study, and 4) the overdose occurs during the 12-month observation period.

A patient is eligible for identification in a physician notification if s/he (a) has been prescribed an opioid by an eligible clinician (b) has a documented overdose event in EHR or mortality data. Patients without overdose events will be excluded. Patients with fatal overdoses in Los Angeles County will be excluded to avoid redundancy with existing notification practices.

[figure not shown]
d) Duration of intervention:

The duration of the overdose notification intervention is one day.

e) Total duration which study will be performed (data collection, intervention, and analysis period):

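### Section D names no contrast from Eq. 1 that estimates the pre-to-post effect in Hypothesis 1, and the coefficient it does name is a fatal-minus-nonfatal difference in slopes

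*Combined protocol and SAP*

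**What the plan says.** **The question.** Under Primary hypotheses (section B.a), clinicians in the notification arm "will exhibit a greater reduction in weekly MME from the pre- to post-period compared to clinicians randomized to the control group"; both overdose types are covered. The Study Synopsis says the same of the measurement: "we will measure the change in clinician weekly milligram morphine equivalent (MME) prescribed to all of their patients in 6-month periods before and after" the letter. Section B.e sets a 6-month pre-period, a 30-day washout after the letter, and then a 6-month post-period.

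**The primary model.** Section D opens with a pre-to-post aim and an intent-to-treat difference-in-differences regression. It then describes a Poisson mixed model with a knotted spline: "This model places a knot at the intervention start date allowing slopes before and after the introduction of the intervention to vary" by group. In Eq. 1, Time "is the study week indexed by j". The post-letter term is a truncated line, equal to weeks since the knot after the knot "and 0 otherwise to allow for nonlinear trends in prescribing following the intervention".

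**The named estimator.** "The coefficient for the group assignment, overdose type, and time interaction, also known as the difference-in-differences estimator" is the only description of the treatment effect, and it is not tied to a numbered β.

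**The secondary model.** In Eq. 2, for high-dose prescribing, Time "is the study period (pre- vs. post-intervention) indexed by j". There the contrast is spelled out: "We will compute the estimated pre- to post-intervention change in the mean proportion of high dose patient visits", for each of four arm-by-type groups. Section D has no matching sentence for the primary outcome.

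**The concern.** The hypothesis concerns a difference between two period averages. Every group-by-time term in Eq. 1 is a weekly slope or a change in slope, and the fitted curve is continuous at the knot, so it cannot show an immediate shift in level. The one coefficient that Section D calls the difference-in-differences estimator also involves overdose type, so it compares the letter's effect between types and does not measure the effect itself.

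An analyst following Section D literally would test a quantity that can be zero while the letter works well. An analyst who sees the problem would have to choose among several terms or combinations after the fact, and these can disagree in size and even in sign. The primary result would then depend on a choice that the plan leaves open.

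**Working it through.** The plan gives no power, effect size or time course for this outcome, so there is no figure to reproduce. The first two steps follow from the printed equation alone. Steps 3 and 4 are illustrations under assumptions.

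**Step 1: what each term means.** Let T be the study week measured from the letter and K the truncated line. On the log scale, the letter-minus-control difference in Eq. 1 is

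- nonfatal: β4 + β7·T + β8·K
- fatal: (β4 + β6) + (β7 + β11)·T + (β8 + β12)·K

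So β7 is the pre-knot slope difference and β8 the slope-change difference, both for nonfatal clusters only. β11 and β12 are the fatal-minus-nonfatal differences in those two quantities. If the letter has the same time course in both types, the T and K parts of the two lines are equal and β11 = β12 = 0, whatever the size of the effect.

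**Step 2: the contrast that Hypothesis 1 needs.** For nonfatal clusters, the mean post-minus-pre difference implied by Eq. 1 is β7 × (mean T post − mean T pre) + β8 × (mean K post). With 26 weeks on each side and the knot at the letter date:

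- no gap: 26·β7 + 13·β8
- washout excluded (30/7 = 4.3 weeks): 30.3·β7 + 17.3·β8

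For fatal clusters, β7 + β11 and β8 + β12 take their places. Section D specifies neither combination.

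**Step 3: what Eq. 1 returns for known effects.** Poisson log-link fits to noise-free weekly means, knot at the letter date:

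- Sustained 10% drop, no gap: β7 = −0.292% and β8 = −0.024% per week. Implied contrast: 26 × (−0.292) + 13 × (−0.024) = −7.90 log-percent, or −7.6%, against a true −10%.
- Sustained 10% drop, washout excluded: β7 = −0.224% and β8 = −0.100%. Implied contrast: 30.3 × (−0.224) + 17.3 × (−0.100) = −8.5 log-percent, or −8.2%.
- 10% drop fading to nil by the end of follow-up, washout excluded: β8 = +0.261% per week (wrong sign). Implied contrast −2.4%, against a true −4.4%.

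In the sustained cases most of the drop is fitted as a pre-letter decline that did not occur, because the curve cannot jump.

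**Step 4: power.** Linear model on the between-arm weekly difference, independent weeks. The effect is scaled so that a simple pre/post contrast has 90% two-sided power, that is, an expected z of 1.96 + 1.28 = 3.24. Other terms follow from the ratio of their expected z to that of the simple contrast. For a sustained drop with washout excluded:

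- β8: ratio 0.056, expected z = 0.056 × 3.24 = 0.18. Power = Φ(0.18 − 1.96) + Φ(−0.18 − 1.96) = 0.038 + 0.016 = 5.4%.
- Mean contrast from Eq. 1: ratio 0.898, expected z = 2.91. Power = Φ(2.91 − 1.96) = 83%.

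The same method for other shapes, knot at the letter date (ranges cover an effect starting at the letter or at the end of washout):

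| Assumed effect | Quantity | No gap | Washout excluded |
|---|---|---|---|
| Sustained drop | β8: power | 5.0% | 5.4% |
| Sustained drop | Mean contrast: power | 80% | 83% |
| Sustained drop | Mean contrast: share recovered | 75% | 81% |
| Fade to nil over 26 weeks | β8: significant increase | 46% | 31% to 52% |
| Fade to nil over 26 weeks | Mean contrast: share recovered | 50% | 46% to 55% |
| Fade to nil over one year | β8: significant increase | 9% | 6% |
| Decline over 13 to 26 weeks | β8: power, right sign | 24% to 46% | 10% to 45% |

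For the gradual declines, the mean contrast recovers 88% to 106% of the effect.

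**Knot position.** Section D puts the knot at the start of the intervention and does not say whether that is the letter date or the end of washout. With the knot at the end of washout, β8 for a sustained drop changes sign (power still about 5%), and the 26-week fade gives a significant increase 61% to 83% of the time.

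**The case against.** **The intention is stated.** A reader might infer that the plan never meant a pre-to-post comparison for the primary outcome. The documents do not support that: the Study Synopsis and the opening of Section D both state one. What is missing is the contrast from Eq. 1 that delivers it.

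**Eq. 1 is not blind to an abrupt effect.** A mean contrast from Eq. 1 has the right sign and 80% to 83% power for a sustained drop, and a joint test of β7 and β8 has 71% to 74%. The letters advise slow tapers (Appendices 2 and 3) and B.e expects delay in opening them, so a gradual decline is plausible. For that shape the mean contrast is close to unbiased, and a spline without a jump is defensible. This stands. But Section D plans neither analysis, the joint test gives no effect size, and the mean contrast understates abrupt or fading effects.

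**The power figures are not those of the named test.** They concern β8, which Section D does not name as the test. That is correct, and they show only what one likely substitute would do. The case against the named three-way term is algebraic and needs no assumed shape. Frequent sign reversal needs an effect that is largely gone within the 26-week window.

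**Washout.** A reader might infer that its handling is undefined. B.e already places those 30 days in neither period. Only its application in the model and the knot position remain to be stated.

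**Overdose type.** Hypothesis 1 covers fatal and non-fatal overdoses, which may mean type-specific effects. The documents do not require an average over types.

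**Conclusion.** The point holds on the documents. Section D specifies no contrast from Eq. 1 that estimates the effect in Hypothesis 1. The coefficient it names is zero under a common letter effect, so it can test only whether the effect differs by overdose type. β7 and β8 do not fill the gap: each is a slope quantity for nonfatal clusters only.

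The size of the harm depends on what would be tested instead and on the time course, neither of which the documents give. With the knot at the letter date and the assumptions of step 4, β8 has about 5% power for a sustained drop and a 31% to 52% chance of a significant result in the wrong direction for a 26-week fade. A derived mean contrast loses 19% to 25% of a sustained drop and about half of a 26-week fade, and little or nothing of a gradual decline. These figures ignore random effects and zero inflation. They should not be read as forecasts for this trial.

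The plan should be corrected before the primary analysis, because the primary hypothesis has no specified estimate that answers it.

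**What to change.** 1. Name one primary estimate for the primary outcome: the letter-minus-control difference in pre-to-post change. Obtain it either from a pre/post indicator model built like Eq. 2, or from Eq. 1 with Post, Post × Group and their overdose-type interactions added.
2. If Eq. 1 is extended, specify the average post-minus-pre contrast. The Post × Group coefficient alone is only the jump at the start of the post segment, with 37% (no gap) or 30% (washout excluded) power for a sustained drop in the same calculation.
3. Report the contrast for nonfatal and for fatal clusters. If one overall answer to Hypothesis 1 is wanted, also report the average over types with weights fixed in advance.
4. State that the three-way coefficient tests only whether the effect differs by type.
5. Carry the B.e washout into the model (those weeks in neither period) and state where the knot sits.
6. Keep the knotted spline as a secondary description of the time course.

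**Cost.** SAP wording and a model of similar or lower complexity on the same data. The indicator model does not adjust for chance differences in pre-period trend, though the secondary spline can show them. It also has slightly less power than a spline-based mean contrast for most gradual declines (90% against 89% to 97%). The documents, dated September 18, 2025, do not say whether outcome data have been seen. If they have, date the change and report both models.
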